Injection-site pain based on VAS (hour)		0, 0.5, 1, 3, 6	24												Performed for both injections of lyophilized formulation into the lower quadrants (ie, first 2 injections), and for the first injection of solution formulation (administered to a lower quadrant). 0 hour assessments to be performed within 1 minute following injection. Time allowance for 0.5 and 1 hour will be $\pm 5$ minutes and all other time allowances will be $\pm 15$ minutes.
Injection-site leakage and bleeding assessment (hour)		0													Performed for both injections of lyophilized formulation into the lower quadrants (ie, first 2 injections), and for the first injection of solution formulation (administered to a lower quadrant). 0 hour assessments to be performed within 1 minute following injection.
LY3074828 pharmacokinetic sampling (hour)		0, 2, 6	24	72	168	240	336	504	672	1008	1344	1680	2016		Times with respect to start of dosing. 0 hour collection immediately (within 15 minutes) before dosing. Time allowance for 2, 6, and 24 hour timepoints: $\pm 15$ , $\pm 30$ , and $\pm 90$

Procedure	Screening	Days													Comments	
		$\leq 28$ days	-1	1	2	4 $\pm 1$ d	8 $\pm 1$ d	11 $\pm 1$ d	15 $\pm 2$ d	22 $\pm 2$ d	29 $\pm 2$ d	43 $\pm 2$ d	57 $\pm 3$ d	71 $\pm 3$ d	85/ED $\pm 3$ d	
Immunogenicity sample																minutes respectively.
Pharmacogenetics sample		X														LY3074828 antibody sample.

Abbreviations: AE = adverse event; BMI = body mass index; CRU = clinical research unit; d = day; ECG = electrocardiogram; ED = early discontinuation; FSH = follicle-stimulating hormone; ICF = informed consent form; TB = tuberculosis; VAS = visual analog scale.

Site should schedule activities as appropriate. In cases where several study procedures are scheduled at the same time, follow this order of priority for procedures: pharmacokinetic samples, ECG, vital signs, clinical laboratory tests, VAS, injection-site leakage assessment, injection-site assessment, immunogenicity sample, stored sample, such that PK sample collection occurs as close to the nominal collection time as possible. Procedures specified as predose may be performed within 2 hours from planned dosing.

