**Table AMAE.2. Treatments Administered**

Treatment arm	Lyophilized formulation CCI [REDACTED]	Pre-filled syringes CCI [REDACTED]	Pre-filled syringes CCI [REDACTED]
Reference/test	Reference	Test 1	Test 2
Product	LY3074828	LY3074828	LY3074828
Dose	CCI [REDACTED] a	CCI [REDACTED]	CCI [REDACTED]
Concentration	CCI [REDACTED]	CCI [REDACTED]	CCI [REDACTED]
Injection volumes	CCI [REDACTED] CCI [REDACTED] CCI [REDACTED]	CCI [REDACTED] CCI [REDACTED]	CCI [REDACTED] CCI [REDACTED]
Number of injections	3	2	4
Formulation and presentation	Lyophilized powder for reconstitution	Solution in a PFS	Solution in a PFS

Abbreviations: PFS = pre-filled syringe.

a Theoretical total dose = 252 mg

Injection-sites selected for SC administration should be in the abdominal region approximately 5 cm from the umbilicus, and treatment should be administered with the needle applied at approximately 45 degrees with pinching the skin. Subcutaneous administration of LY3074828 should be given by a limited number of individuals for consistency. The same type of syringe and needle (27-gauge, half-inch needle) should be used for all subjects to ensure all injections are delivered to a consistent depth target into the SC space. Subsequent injection(s) should be given immediately following the previous injection.

For the lyophilized formulation (Reference), the [CC1] injection and the first of the [CC1] injections will be given into lower quadrants of the abdomen. The remaining [CC1] injection will be administered into an upper quadrant. The order and location of the first 2 injections will be randomized (see Section 7.2).

For administration of the [CC1] solution formulation in PFSs (Test 1), injections will be given into separate lower quadrants of the abdomen. For administration of the [CC1] solution formulation in PFSs (Test 2), the first 2 injections will be given into separate lower quadrants of the abdomen, and the final 2 injections will be given into separate upper quadrants of the abdomen.

Further information around SC administration will be in pharmacy handling instructions.

Investigational products will be prepared at the site by pharmacists or other trained personnel. Investigational products will only be administered to subjects on-site by nurses or other appropriately trained personnel.

The investigator or designee is responsible for:

- explaining the correct use of the investigational products to the site personnel
- verifying that instructions are followed properly

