#### 10.3.2.2. Pharmacokinetic Statistical Inference

Pharmacokinetic parameter estimates will be evaluated to delineate effects of formulation. Log-transformed DN- $AUC(0-\infty)$ , DN- $AUC(0-t_{last})$ , and DN- $C_{max}$  will be evaluated in a linear fixed-effects model with a fixed effect for formulation. For the primary endpoint, a model comparing the differences between the [REDACTED] LY3074828 solution formulation and the [REDACTED] LY3074828 lyophilized formulation will be used. For the secondary endpoints, a model comparing the differences between the [REDACTED] LY3074828 solution formulation and the [REDACTED] LY3074828 lyophilized formulation, and between the [REDACTED] and [REDACTED] LY3074828 solution formulations will be used. Differences will be back-transformed to present the ratios of geometric least squares means and the corresponding 90% CI. If leakage occurs frequently, whether injection-site leakage occurred (yes/no) may also be included as a covariate in the model. Furthermore, if leakage is found to be significant, the amount of leakage will also be added to the model.

The  $t_{max}$  will be analyzed using a Wilcoxon rank sum test. Estimates of the median difference, 90% CIs, and p-values from the Wilcoxon rank sum test will be calculated.

Additional PK analyses may be conducted if deemed appropriate.

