9.3.2 Pharmacokinetic Statistical Methodology

Log-transformed DN-AUC($0-\infty$), DN-AUC($0-t_{last}$), and DN- C_{max} will be evaluated in a linear fixed-effects model with a fixed effect for formulation. If leakage occurs frequently, whether injection-site leakage occurred (yes/no) may also be included as a covariate in the model. Furthermore, if leakage is found to be significant, the amount of leakage will also be added to the

model. The formulation differences will be back transformed to present the ratios of geometric least squares means and the corresponding 90% CI.

A single linear model with contrasts will be used for all of the following comparisons:

- Primary objective: CCI LY3074828 PFS solution formulation versus CCI LY3074828 lyophilized formulation
- Secondary Objective: CCI LY3074828 PFS solution formulation versus CCI LY3074828 PFS solution formulation
- Secondary Objective: CCI LY3074828 PFS solution formulation versus CCI LY3074828 lyophilized formulation

Example SAS code:

```
proc mixed data=xxx;
  by parameter;
  class formulation ISLoccur;
  model log_pk = formulation ISLoccur ISLamount / residual;
  lsmeans formulation / alpha=0.1 cl pdiff;
  ods output lsmeans=lsmeans;
  ods output diffs=diffs;
run;
```

The tmax will be analyzed using a Wilcoxon rank sum test for all of the above comparisons. Estimates of the median difference, 90% CIs, and p-values from the Wilcoxon rank sum test will be calculated.

Additional PK analyses may be conducted if deemed appropriate.

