9.4.8 Injection Site Leakage

For the lyophilized formulation, injection-site assessments of leakage will be performed for the 2 injections in the lower quadrants of the abdomen (1.0 mL and 1.5 mL injections). For both dose levels of solution formulation in PFSs, injection-site assessments of leakage will be performed for the first injection, which will be administered into a lower quadrant of the abdomen.

Injection site leakage data will be listed. Any bleeding from injection site will also be documented and listed.

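### The primary bioavailability model may be adjusted for injection-site leakage, a post-injection outcome recorded unevenly across arms, and neither document keeps the formulation-only ratio as the primary result

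*SAP*

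**What the plan says.** SAP 9.3.2 says the log-transformed dose-normalized AUC(0-∞), AUC(0-tlast) and Cmax "will be evaluated in a linear fixed-effects model with a fixed effect for formulation". It then allows an extension: "If leakage occurs frequently, whether injection-site leakage occurred (yes/no) may also be included as a covariate in the model". Protocol 10.3.2.2 has the same option and continues that "if leakage is found to be significant, the amount of leakage will also be added to the model". Neither document says how often is frequent or at what level leakage is significant.

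The extension reaches every bioavailability comparison: "A single linear model with contrasts will be used for all of the following comparisons", namely the primary and both secondary contrasts. The only code shown contains both leakage terms: "model log_pk = formulation ISLoccur ISLamount / residual".

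Leakage is measured by blotting the site after the injection (Protocol 9.4.6) and is listed as an exploratory endpoint in Table AMAE.1. The Schedule of Activities restricts the assessment: "Performed for both injections of lyophilized formulation into the lower quadrants (ie, first 2 injections), and for the first injection of solution formulation". SAP 9.4.8 agrees; for both solution arms, "injection-site assessments of leakage will be performed for the first injection, which will be administered into a lower quadrant of the abdomen". Protocol 5.1 gives three, two and four injections in Reference, Test 1 and Test 2.

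The two assessed Reference injections are 1.5 mL and 1.0 mL (Protocol 9.4.6), and Protocol 7.1 adds: "The order and location of the first 2 injections will be randomized".

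No sentence in either document says that the formulation-only ratio remains primary, or is reported beside an adjusted one, once a leakage term has entered.

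**The concern.** Leakage is not a baseline covariate. If formulation, presentation or injection volume affects how much drug leaks out, that loss is part of the relative bioavailability of the product as administered. Conditioning on leakage removes some of it, and the contrast becomes a ratio at equal recorded leakage, which is not the stated primary objective. Part of the leakage may instead reflect technique or the subject, but the model cannot separate the two.

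The covariate also means different things in different arms, because a different share of injections is observed in each. The SAP does not say how the yes/no variable is coded when a Reference subject has two assessed injections. If only the first injection given counted, the Reference value would mix 1.5 mL and 1.0 mL injections, since their order is randomized. Two analysts could both follow the SAP and report different headline ratios.

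The estimate will be used. Protocol 10.3.7 says the data review is meant to start manufacturing steps for the formulation and to inform Phase 3 dose selection.

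**Working it through.** **1. The planned precision.** SAP 7 gives CV 49%, 16 evaluable subjects per arm, a 90% CI, and 90% probability that the half-width on the log scale is at most 0.32. The log SD is √ln(1 + 0.49²) = 0.4639. The 90th-percentile half-width is t(0.95, df) × 0.4639 × √(2/16) × √(χ²(0.90, df)/df).

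- Two-arm variance, df 30: 0.322, with P(half-width ≤ 0.32) = 0.888.
- Three-arm formulation-only model, df 45: 0.311, with P = 0.941.

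The stated 0.32 is reproduced. There is no sample-size error.

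**2. Unequal observation.** The shares assessed are 2/3 = 67%, 1/2 = 50% and 1/4 = 25%. Assume every injection in every arm leaks with probability 30%.

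- Recorded any-leak: 1 − 0.7² = 51% in Reference and 30% in each Test arm.
- True any-leak: 1 − 0.7³ = 66%, 1 − 0.7² = 51% and 1 − 0.7⁴ = 76%.

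Under any-leak coding the covariate differs by arm although leakage per injection does not.

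**3. Effect on the ratio and its precision.** Leak rates, losses and the coding rule are assumptions, because the documents give none. Test 1 versus Reference is taken as the contrast of interest, because the dose labels are blacked out. The simulation setup was:

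- three-arm linear model on log AUC, 16 per arm, SD 0.4639, 40,000 trials per scenario, yes/no term only;
- Reference 1.5 + 1.0 + 1.0 mL, with the 1.5 mL and one 1.0 mL injection observed; Test 1 two equal injections and Test 2 four, first observed;
- independent leaks, a fixed fraction of the injection lost per leak, the same leak rate in both Test arms, and no other formulation effect.

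Any-leak coding counts a Reference subject as yes if either observed injection leaks. First-injection coding counts only the first one given, which is 1.5 or 1.0 mL with equal chance. Both codings were applied to the same simulated data.

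Check for 50% versus 20% leakage and 30% loss:

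- Test 1 mean log exposure: 0.32 × ln 0.85 + 0.04 × ln 0.70 = −0.066.
- Reference mean log exposure over its eight equally likely leak patterns: −0.168.
- True log-ratio: −0.066 + 0.168 = 0.102. The simulated unadjusted mean is 0.101.

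Each cell below gives the mean log-ratio, then P(half-width ≤ 0.32).

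| Leak rate, Reference / Tests | Loss per leak | Formulation only | Adjusted, any-leak | Adjusted, first-injection |
|---|---|---|---|---|
| 50% / 20% | 30% | 0.101, 92% | 0.024, 50% | 0.063, 80% |
| 50% / 20% | 10% | 0.031, 94% | 0.007, 53% | 0.019, 82% |
| 20% / 50% | 30% | −0.106, 91% | −0.087, 88% | −0.066, 81% |
| 30% / 20% | 30% | 0.032, 92% | −0.009, 79% | 0.020, 89% |
| 20% / 20% | 30% | −0.002, 92% | −0.022, 88% | −0.001, 91% |
| 20% / 20% | 10% | −0.001, 94% | −0.007, 89% | 0.000, 92% |
| 50% / 50% | 30% | −0.002, 90% | −0.037, 84% | −0.002, 89% |
| 50% / 50% | 10% | 0.000, 94% | −0.010, 87% | 0.000, 92% |

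The Monte Carlo standard error of a mean log-ratio is about 0.001. In the first row the ratios are exp(0.101) = 1.11 unadjusted, against exp(0.024) = 1.02 or exp(0.063) = 1.07 adjusted. The mean half-widths in that row are 0.279, 0.325 and 0.293. In a single trial under that row, adjusted and unadjusted log-ratios differ in absolute value by 0.10 (any-leak) or 0.05 (first-injection) on average.

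**4. The amount term.** At an assumed p < 0.05 threshold, the yes/no term is significant in 11–16% of trials at 30% loss and about 6% at 10% loss. On that reading the amount would seldom be added. Its effect was not quantified.

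**The case against.** The stated default is formulation only. The first step is optional, was written down in advance, and its trigger does not use PK results. The code is labelled as an example. If leakage is rare, nothing changes. All of this is right and makes the problem conditional.

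One can also argue that adjustment fits the aim of isolating formulation effects. Leakage lowers the delivered dose, the outcomes are already dose-normalized, and Protocol 7.1 treats technique as something to hold constant. That is a legitimate secondary question. It is not the ratio named as the primary endpoint, and the covariate misses at least one injection per subject in every arm.

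The assumed inputs can be called severe: 30% loss means 0.45 mL of a 1.5 mL injection. At 10% loss the largest mean shift is 0.031 − 0.007 = 0.024, against a half-width of about 0.27. The fall to 50% reflects a mean half-width of 0.325, only just above 0.32. The point about estimates therefore stands for small losses. The precision loss does not go away, because it comes mainly from imbalance of the covariate between arms.

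Any-leak is arguably the natural reading of the yes/no variable. The SAP does not say so, and in the first row that reading does the most harm.

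Finally, the table, figure and listing shells mentioned in SAP 3 are not available and might show both ratios. The finding is limited to the SAP and protocol text. For a single questionable datum within a profile, SAP 9.3.1 does require results with and without it; 9.3.2 has no matching rule for its headline model.

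**Conclusion.** The concern holds. Both documents allow a post-injection outcome, observed on unequal shares of injections, into the single model behind all three comparisons, with undefined triggers and no coding rule. Neither protects the formulation-only ratio.

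The size depends on assumed leak rates and losses. It ranges from negligible (equal rates with first-injection coding) to a mean shift of 0.101 − 0.024 = 0.077 on the log scale, with the assurance of the 0.32 half-width falling from 92% to 50% (50% versus 20% leakage, 30% loss, any-leak coding). A milder 30% versus 20% contrast at 30% loss still lowers it from 92% to 79% under any-leak coding.

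No equivalence limit is stated, so no pass/fail conclusion changes. The harm is an ambiguous headline estimate and possible loss of planned precision. It should be fixed, because the remedy is nearly free.

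**What to change.** In SAP 9.3.2, name the formulation-only model as the primary and secondary analysis for DN-AUC(0-∞), DN-AUC(0-tlast) and DN-Cmax, and delete ISLoccur and ISLamount from that code. Report any leakage-adjusted model only as a labelled sensitivity analysis, beside the unadjusted ratio. For that analysis, define when it is run and when the amount is added, state how the yes/no variable is coded for the two assessed Reference injections, and note that only some injections were observed. Record the change in SAP 11, which now declares none.

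The cost is SAP wording and two code terms. No new data are needed, and no protocol amendment, because SAP 3 says the SAP supersedes the protocol's statistical considerations. The price is that leakage can no longer explain exposure variability in the headline model.

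A minor separate item: SAP 9.4.8 only lists leakage data, whereas Protocol 10.3.6 plans a summary by treatment. The two should be reconciled unless the output shells already contain that table.

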9.4 Safety and Tolerability Assessments

9.4.1 Adverse events

Where changes in severity are recorded in the Case Report Form (CRF), each separate severity of the adverse event (AE) will be reported in the listings, only the most severe will be used in the summary tables. A pre-existing condition is defined as an AE that starts before the subject has provided written informed consent and is ongoing at consent. A non-treatment emergent AE is defined as an AE which starts after informed consent but prior to dosing. A treatment-emergent AE is defined as an AE which occurs postdose or which is present prior to dosing and becomes more severe postdose

All AEs will be listed. Treatment-emergent AEs will be summarized by treatment, severity and relationship to the study drug. The frequency (the number of AEs, the number of subjects experiencing an AE and the percentage of subjects experiencing an AE) of treatment-emergent AEs will be summarized by treatment, Medical Dictionary for Regulatory Activities (MedDRA) version 20.0 system organ class and preferred term. The summary and frequency AE tables will be presented for all causalities and those considered related to the study drug. Any serious AEs will be tabulated.

9.4.2 Concomitant medication

Concomitant medication will be coded using the World Health Organization (WHO) drug dictionary (Version December 2016). Concomitant medication will be listed.

9.4.3 Clinical laboratory parameters

All clinical chemistry and hematology data will be summarized by parameter and treatment, and listed. Urinalysis data will be listed. Additionally clinical chemistry, hematology and urinalysis data outside the reference ranges will be listed.

Values for any clinical chemistry, hematology and urinalysis values outside the reference ranges will be flagged on the individual subject data listings.

9.4.4 Vital signs

Vital signs data will be summarized by treatment together with changes from baseline, where baseline is defined as Day 1 predose. Figures of mean vital signs and mean changes from baseline profiles will be presented by treatment. Furthermore, values for individual subjects will be listed.

9.4.5 Electrocardiogram (ECG)

ECGs will be performed for safety monitoring purposes only and will not be presented.

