#### **9.4.3. *Electrocardiograms***

For each subject, a single 12-lead digital ECG will be collected according to the Schedule of Activities (Section 2). Electrocardiograms must be recorded before collecting any blood for safety or PK tests. Subjects must be supine for at least 5 minutes before ECG collection and remain supine but awake during ECG collection. Electrocardiograms may be obtained at additional times, when deemed clinically necessary by the investigator. All ECGs recorded should be stored at the investigational site.

Electrocardiograms will be interpreted by a qualified physician (the investigator or qualified designee) at the site as soon after the time of ECG collection as possible, and ideally while the subject is still present, to determine whether the subject meets entry criteria at the relevant visit(s) and for immediate subject management, should any clinically relevant findings be identified.

If a clinically significant finding is identified (including, but not limited to, changes in QT/corrected QT [QTc] interval from baseline) after enrollment, the investigator will determine if the subject can continue in the study. The investigator, or qualified designee, is responsible for determining if any change in subject management is needed, and must document his/her review of the ECG printed at the time of collection. Any new clinically relevant finding should be reported as an AE.

Any clinically significant findings from ECGs that result in a diagnosis and that occur after the subject receives the first dose of the investigational product, should be reported to Lilly, or its designee, as an AE via eCRF.

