#### 10.3.1.2. Statistical Evaluation of Safety

Safety parameters that will be assessed include clinical laboratory parameters, vital signs, and ECG parameters. The parameters, and changes from baseline (predose) where appropriate, will be listed, and summarized using standard descriptive statistics. Additional analysis will be performed if warranted upon review of the data.

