11. CHANGES FROM THE PROTOCOL SPECIFIED STATISTICAL ANALYSES

There were no changes from the protocol specified statistical analyses.

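### SAP Section 11 declares no change from the protocol, but SAP 9.4.5 removes the ECG listing and summary; the readable SAP also plans no by-arm leakage summary

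*SAP*

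**What the plan says.** **ECG.** Protocol Section 10.3.1.2 states: "Safety parameters that will be assessed include clinical laboratory parameters, vital signs, and ECG parameters". It continues: "The parameters, and changes from baseline (predose) where appropriate, will be listed, and summarized using standard descriptive statistics". The SAP takes the three groups in turn:

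- Laboratory data, SAP 9.4.3: "All clinical chemistry and hematology data will be summarized by parameter and treatment, and listed".
- Vital signs, SAP 9.4.4: "Vital signs data will be summarized by treatment together with changes from baseline, where baseline is defined as Day 1 predose".
- ECG, SAP 9.4.5: "ECGs will be performed for safety monitoring purposes only and will not be presented".

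**Declaration.** SAP Section 11 reads: "There were no changes from the protocol specified statistical analyses". SAP Section 3 gives the SAP precedence over the protocol's statistical section and undertakes to point out considerations that differ substantially.

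**Leakage.** Protocol Section 10.3.6 commits to a descriptive summary of leakage for each treatment. Table AMAE.1 puts the incidence of leakage in an exploratory endpoint, and SAP 4.3 keeps the matching objective. SAP 9.4.8 provides for a listing and mentions no summary. SAP 9.1 restricts summary statistics to data for which the SAP spells them out.

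**The concern.** Section 11 is where a reader of the SAP or the study report looks to learn how the analysis departs from the protocol. It says nothing departed, yet one of the three safety parameter groups that the protocol promised to list and summarize is removed a few pages earlier. Someone relying on Section 11 alone would be misinformed. Followed as written, the report would hold neither a listing nor a summary of ECG parameters.

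Leakage raises a similar question with less certainty. If the readable text is the whole plan, the exploratory leakage endpoint gets no result by arm, only subject-level data in a listing.

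**Working it through.** The plan states no figure on this point, so there is none to reproduce. The check is a comparison of text, followed by a count of the data affected.

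**Step 1. Protocol against SAP.**

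| Item | Protocol | SAP | Shown in SAP Section 11? |
|---|---|---|---|
| Laboratory | list and summarize (10.3.1.2) | chemistry and hematology summarized and listed (9.4.3) | not needed |
| Vital signs | list and summarize (10.3.1.2) | summarized with change from baseline, and listed (9.4.4) | not needed |
| ECG | list and summarize (10.3.1.2) | not presented (9.4.5) | no |
| Leakage | descriptive summary by arm (10.3.6) | listing only, on the readable text (9.4.8 with 9.1) | no |

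The ECG row is a direct conflict, and every text involved is unredacted. If 9.4.5 is followed, Section 11 is false.

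The leakage row is an inference from silence combined with the rule in SAP 9.1. The SAP's usage elsewhere supports a literal reading of a listing. In 9.4.3, chemistry and hematology are both summarized and listed while urinalysis is only listed, and 9.4.9 adds frequency tables to the immunogenicity listing in so many words. The inference is still incomplete, because the content of 9.4.6 and 9.4.7 is blacked out and SAP Section 3 refers to a separate shell document for the detailed description of outputs.

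**Step 2. ECG recordings covered.** Inputs: the ECG row of the Schedule of Activities (Protocol Section 2), with one ECG per time point, and 54 subjects (Protocol 5.1).

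- Day 1 predose: 1
- Timed postdose at 2, 6, 24, 72, 168, 336, 672 and 1344 hours: 8
- Day 85 or early discontinuation: 1
- Per subject: 1 + 8 + 1 = 10
- All subjects: 10 × 54 = 540, of which 9 × 54 = 486 are postdose

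The screening ECG is left out, and full attendance is assumed.

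**Step 3. Leakage assessments covered.** Inputs: Protocol 9.4.6 and SAP 9.4.8 (two assessed injections per Reference subject, one per solution subject), and 18 subjects per arm.

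- Reference: 18 × 2 = 36
- Test 1: 18 × 1 = 18
- Test 2: 18 × 1 = 18
- Total: 36 + 18 + 18 = 72

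No leakage rate is assumed. Both counts describe how much data the outputs would cover; they do not measure consequence.

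**The case against.** The strongest reply on ECG is that SAP Section 3 lets the SAP supersede the protocol, that only substantial differences need be flagged, and that the omission is stated openly under its own heading. Much of this stands. Dropping the output is within the sponsor's power, and whether it is substantial is a matter of judgement. But Section 11 is not limited to substantial changes; it says there were none. SAP 9.4.5 does not describe itself as a departure and does not refer to the protocol text that it replaces.

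It is also fair to say that the practical effect is small. Under Protocol 9.4.3 a physician at the site reads each ECG, and "Any new clinically relevant finding should be reported as an AE". SAP 9.4.1 lists all adverse events. A reader might infer that ECG safety signals would be hidden from the report, and the documents do not support that. What is lost is the listing and the descriptive summary of the parameters.

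On leakage, the reply is that silence is not omission, and this stands as a limit on confidence. Three stronger readings are tempting and should be resisted:

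- A reader might infer that the summary has definitely been dropped. It could sit in the redacted 9.4.6 or 9.4.7, or in the shells.
- A reader might infer that the listing-only default in SAP 9.4.11 settles the matter. That default covers safety assessments not detailed in Section 9.4, and leakage has its own subsection. Only the general rule in SAP 9.1 bears on it.
- A reader might infer that no planned table would support the judgement in SAP 9.3.2 on whether leakage is frequent enough to become a covariate. The shells are unseen, and leakage in the assessed injections could be counted from the planned listing.

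**Conclusion.** The point holds as a minor reporting correction.

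- **ECG against Section 11: high confidence.** The declaration is wrong as written. One of three protocol-specified parameter groups is removed, covering 540 scheduled recordings from Day 1 predose onward under full attendance.
- **Leakage: moderate confidence.** On the readable text, a protocol-specified by-arm summary covering 72 assessed injections is not planned. This rests on the assumption that neither the redacted sections nor the shells contain it.

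No primary or secondary PK result changes, and leakage stays available as a possible covariate in the PK model (SAP 9.3.2).

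**What to change.** 1. **SAP 9.4.5:** restore the ECG listing and descriptive summary, with changes from predose where appropriate, as Protocol 10.3.1.2 specifies. If the sponsor keeps the omission, declare and justify it in Section 11.
2. **SAP 9.4.8:** unless already planned elsewhere, add a descriptive summary by arm of leakage incidence and amount. Report it per assessed injection and show the denominators, because Reference subjects contribute two and solution subjects one.
3. **SAP Section 11:** replace the blanket statement with a list of the departures that remain after steps 1 and 2. A smaller wording change can be settled in the same pass: the relation between antibodies and PK is a commitment in Protocol 10.3.5 but optional in SAP 9.4.9.

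The cost is SAP wording plus one descriptive leakage table from data already collected. Declaring the ECG omission needs wording only. Restoring the ECG output costs more if the measurements are not already in the database. The documents do not say whether they are; if they are, 9.4.5 also conflicts with the general promise in SAP 9.1 to list everything databased.
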